6.2.5.5 Assessment of Severity

The severity of an AE refers to the extent to which an AE affects the subject's daily activities. All solicited AEs will be graded according to the FDA Toxicity Grading Scale (Appendix 3, Section 12.3) and entered into the AE reporting page. Grade 1-3 hematology or serum chemistry values determined by the investigator to be clinically significant will be entered into the AE reporting page. An FDA toxicity Grade 2 (moderate) or greater (ie, $\geq 2.6 \times$ ULN; see Appendix 3, Section 12.3) ALT and/or AST elevation (regardless of investigator-assessed clinical significance) will be entered into the AE reporting page, and the grading will be consistent with the FDA toxicity score. All Grade 4 laboratory findings are considered AEs regardless of the investigator's determination of clinical significance and should also be entered using the FDA toxicity score for severity. In all other cases, the severity of each AE will be rated as mild, moderate, or severe using the following criteria:

Mild:	An event usually transient in nature and generally not interfering with
	normal activities.
Moderate:	An AE that is sufficiently discomforting to interfere with normal
	activities.
Severe:	An AE that is incapacitating and/or prevents normal activities.

Changes in the intensity of an AE should be documented to allow an assessment of the duration of the event at each level of intensity to be performed. Adverse events characterized as intermittent do not require documentation of onset and duration of each episode. The severity of solicited AEs will be classified.

6.2.5.6 Assessment of Causality

The investigator's assessment of the relationship between an AE and study drug is part of the documentation process, but it is not a factor in determining what is or is not reported in the study. If there is any doubt as to whether a clinical observation is an AE, the event should be reported.

Protocol: BP-I-16-005 Version 2.0

The relationship or association of the IP in causing or contributing to the AE will be characterized using the following classification and criteria:

Unrelated: This relationship suggests that there is not a reasonable possibility^a that the AE is related to the IP.

Related: This relationship suggests that there is a reasonable possibility^a that the AE is related to the IP.

Note: The investigator should consider the package inserts of all products administered in this study when determining causality.

^a Reasonable possibility means there is evidence to suggest a causal relationship between the IP and the AE.

6.2.5.7 Assessing Expectedness

Expected AEs are AEs consistent with the applicable product information provided by the sponsor (the investigator brochures for IP). The sponsor, in consultation with the medical monitor, determines expectedness of SAEs and MAAEs. The sponsor and medical monitor should consider the package inserts of all products administered in this study when determining expectedness. If the assessment is that the SAE or MAAE is expected, no further reporting is required. If the medical monitor's assessment is that the SAE or MAAE is unexpected, then the event may represent a SUSAR or expedited SAE for reporting purposes.

6.2.5.8 Follow-Up of Subjects Reporting Adverse Events

All AEs must be reported in detail on the appropriate page in the eCRF and followed to satisfactory resolution, until the investigator deems the event to be chronic or not clinically significant, or until the subject is considered to be stable. In the case of an abnormal laboratory value that is entered as an AE due to toxicity grade parameters (ie, clinically significant Grade 1 to 3, Grade 4 [regardless of clinical significance], and ALT and/or AST elevations $\geq 2.6 \times$ ULN), the subject will be required to have a repeat laboratory test with results assessed by the investigator and continued monitoring until the results return to the screening baseline value (ie, baseline toxicity score) or are considered stable with a new baseline. Subjects may not receive revaccination if ALT and/or AST elevations reach ≥ 2 by FDA toxicity score and do not return to the screening baseline value (ie, baseline toxicity score) by the time of revaccination.

Protocol: BP-I-16-005 Version 2.0

6.3 Immunogenicity Assessments

Immunogenicity assessments will include the following assessments at Day 1, Day 22, Day 43, and Day 142 (Groups A-D, G-J) and at Day 1, Day 22, Day 43, Day 142, Day 163, and Day 262 (Groups E, F, K, L).

- Serum HAI antibody titers
- Seroprotection based on serum HAI antibody titers, defined as an HAI antibody titer ≥1:40
- Seroconversion based on serum HAI antibody titers, defined as either a prevaccination HAI titer <1:10 and a postvaccination HAI titer ≥1:40, or a prevaccination HAI titer ≥1:10 and a minimum 4-fold rise in postvaccination HAI titer
- Serum MN antibody titers
- Seroconversion based on serum MN antibody titers, defined as either a prevaccination MN titer <1:10 and a postvaccination MN titer ≥1:40, or a prevaccination MN titer ≥1:10 and a minimum 4-fold rise in postvaccination MN titer

The details on the handling, processing, and shipping will be provided in the Laboratory Manual.

6.4 Pregnancy

Pregnancy is not regarded as an AE unless there is a suspicion that an IP may have interfered with the effectiveness of a contraceptive medication. Any pregnancy that occurs during study participation must be reported using a clinical study pregnancy form. If a subject becomes pregnant, she will not have any invasive procedures performed and will not receive any further vaccinations, as normally mandated by the protocol. The subject will undergo all other evaluations according to the schedule of events (Table 12–1 and Table 12–2). To ensure subject safety, each pregnancy must be reported to the sponsor, BARDA, within 2 weeks of learning of its occurrence. The pregnancy must be followed up to resolution and 2 weeks after live birth to determine outcome (including spontaneous miscarriage, elective termination, normal birth, or congenital abnormality) and status of mother and child, even if the subject was discontinued from the study or if the pregnancy ends after the end-of-study visit (Visit 9 [Groups A-D, G-J] and Visit 14 [Groups E, F, K, L]). Pregnancy complications

BARDA CSNH5 Influenza Vaccine With Either AS03 or MF59Protocol: BP-I-16-005 Version 2.026 February 2018and elective terminations for medical reasons must be reported as an AE or SAE.Spontaneous miscarriages must be reported as an SAE.

6.5 Sample Collections

Procedures for the handling and processing of biological samples are provided in the Laboratory Manual.

The hematology, coagulation, and chemistry/metabolic panel laboratory analyses will be performed at a central laboratory. Reference ranges will be used by the investigator to assess the laboratory data for clinical significance and pathological changes and will be graded according to the FDA Toxicity Grading Scale (Appendix 3, Section 12.3).

The samples collected for immunogenicity testing and cell-mediated assays will be stored in appropriate conditions as specified in the Laboratory Manual until shipped for testing at a facility designated by the sponsor.

Protocol: BP-I-16-005 Version 2.0

7 Statistical and Analytical Plan

This is a descriptive study and no formal hypotheses for the primary endpoints are being tested. The main purpose of this study is to assess the ability of H5 influenza vaccines and adjuvants present in the NPIVS to generate an immune response to homologous and to antigenically distant heterologous H5 influenza virus strains. The primary outcomes will be descriptive in terms of whether the study vaccines are safe and immunogenic.

7.1 Primary Endpoints

- Safety: Occurrence of mild, moderate, or severe solicited local and systemic reactogenicity symptoms during the 8 days postvaccination, inclusive of the vaccination day
- Immunogenicity: SPR (defined as the proportion of subjects achieving a serum HAI titer of at least 1:40 against influenza antigen) against strains contained in the vaccines on Day 43 for Groups A-D and G-J and on Day 163 for Groups E, F, K, L

7.2 Secondary Endpoints

Secondary Safety Endpoints:

- Occurrence of SAEs, MAAEs, and PIMMCs in 12 treatment groups through 12 months after the last dose of study vaccine
- Occurrence of any AEs leading to study withdrawal
- Frequency and severity of unsolicited AEs for 21 days following each vaccination
- Occurrence of clinical safety laboratory abnormalities at all collected time points
- Occurrence of vital sign abnormalities at all collected time points

Secondary Immunogenicity Endpoints:

- Serum HAI and MN antibody responses at all collected time points
- SPR of serum HAI antibody at collected time points

Protocol: BP-I-16-005 Version 2.0

• Seroconversion rate (defined as proportion of subjects achieving either a prevaccination antibody titer of <1:10 and a postvaccination titer of at least 1:40 or a prevaccination antibody titer of at least 1:10 and a 4-fold or greater increase of postvaccination antibody titer; if antibody titer is undetectable, it will be assigned a value of half the lower limit of detection) at all collected postvaccination time points

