4.3 Revaccination Eligibility

Subjects are free to withdraw from further study vaccination at any time upon request. A subject may not be eligible to receive further study vaccination for any of the following reasons:

- 1. Does not meet the protocol inclusion or exclusion criteria at the time of the second or, if applicable, third vaccination.
- 2. Noncompliance with the protocol.
- 3. Serious or intolerable AE(s) that in the investigator's opinion precludes further study vaccination.

Protocol: BP-I-16-005 Version 2.0

- 4. A serum ALT or AST elevation that is Grade 2 (moderate) or greater based on FDA toxicity grading (ie, ≥2.6 × ULN; see Appendix 3, Section 12.3) regardless of investigator-assessed clinical significance. Note, such an elevated ALT and/or AST value must be resolved on repeat testing to the screening baseline value (eg, baseline toxicity score) before revaccination can occur. Only those subjects who have resolution of the ALT and/or AST elevations within the visit window are eligible for revaccination.
- 5. Other laboratory safety assessments that remain clinically significant prior to planned vaccination.
- 6. Symptoms or an intercurrent illness not consistent with the protocol requirements or that justifies no further study vaccination.
- 7. Other (eg, pregnancy, development of contraindications precluding further study vaccination).

All subjects who discontinue from study treatment prematurely will follow the same visit schedule as other subjects.

5 Study Groups

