5.3.2 Investigational Product Accountability

The investigator will maintain accurate records of receipt of all IP, including dates of receipt. In addition, accurate records will be kept regarding when and how much IP is dispensed and administered to each subject in the study. Reasons for departure from the expected dispensing regimen must also be recorded. At the completion of the study, to satisfy regulatory requirements regarding accountability, all IP will be reconciled and retained or destroyed according to applicable regulations. No IP will be destroyed until authorized in writing by the sponsor.

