7.7.4 Analysis of Secondary Endpoint

7.7.4.1 Analysis of Secondary Safety Endpoint

Serious adverse events, MAAEs, PIMMCs, and AEs leading to study withdrawal will be summarized by study group and system organ class (SOC)/preferred term (PT).

Unsolicited AEs (including clinically significant laboratory and vital sign abnormalities) for 21 days following each vaccination will be summarized by study group, SOC/PT, and further summarized by severity and relatedness.

Clinical safety laboratory abnormalities will be summarized at prevaccination and 7 days after each vaccination by study group.

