10.2.2 Protocol Deviations

The investigator or designee must document and explain in the subject's source documentation any deviation from the approved protocol. The investigator may implement a deviation from, or a change of, the protocol to eliminate an immediate hazard to study subjects without prior IRB approval. As soon as possible after such an occurrence, the implemented deviation or change, the reasons for it, and any proposed protocol amendments should be submitted to the IRB for review and approval, to the sponsor for agreement, and to the regulatory authorities, if required.

A deviation from the protocol is an unintended or unanticipated departure from the procedures or processes approved by the sponsor and the IRB and agreed to by the investigator. A significant deviation occurs when there is nonadherence to the protocol by the subject or investigator that results in a significant, additional risk to the subject or that may affect the study outcome. Significant deviations can include nonadherence to inclusion or exclusion criteria or nonadherence to FDA regulations or ICH GCP guidelines, and may lead to the subject being withdrawn from the study (ie, no longer receive IP, see Section 4.2).

Neither the sponsor nor designee will authorize deviations to the study. Deviations from the protocol are not permitted except to protect the safety of a subject.

```
BARDA CSNH5 Influenza Vaccine With Either AS03 or MF59Protocol: BP-I-16-005 Version 2.026 February 2018Protocol deviations will be documented by the clinical monitor throughout the course of
monitoring visits. Investigators will be notified in writing by the monitor of deviations. The
```

monitoring visits. Investigators will be notified in writing by the monitor of deviations. The IRB should be notified of all significant protocol deviations in a timely manner, as defined by the IRB.

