All AEs reported after the first dose of IP will be summarized in tables. AEs within 21 days of each dose of IP, and before the date and time of the next dose of IP (if applicable) will be summarized in tables based on each dose only (Dose 1, 2 for Groups A-D, G-J; Dose 1, 2, 3 for Group E, F, K and L). When the time of an AE is missing and the AE start date is on the date of vaccination, then that AE will be considered as happening after the corresponding dose of IP.

All AEs will be summarized by presenting the number and percentage of subjects having any AEs and having each individual adverse event based on SOC and PT, and PT only. At each level of subject summarization, a subject is counted once if the subject reported one or more events. Percentages will be calculated out of the number of subjects as treated per study group in the Safety Set. For the dose-specific AE summaries, percentages will be calculated out of the number of subjects as treated per study group corresponding to Dose 1, Dose 2 or Dose 3.

Unless otherwise stated, AEs will be sorted in descending order by frequency of SOC and PT.

The following summaries, based on Dose 1 only, Dose 2 only, and both Dose 1 and Dose 2 for Groups A-D, G-J and Dose 1 only, Dose 2 only, Dose 3 only, and all Dose 1, Dose 2 and Dose 3 for Groups E, F, K and L will be provided:

- Overview summary of the number and percentage of subjects with any AE, SAE, AE related to IP, AE leading to study withdrawal, AE leading to death, solicited local AE, severe solicited local AE, solicited systemic AE, severe solicited systemic AE, MAAE, PIMMC, unsolicited AE, severe unsolicited AE, and unsolicited AE related to IP
- All AEs by SOC and PT
- All AEs by AE Type and PT
- All AEs by SOC, PT and Severity

- All AEs by SOC, PT and Relationship
- All unsolicited AEs by SOC, PT and Day of Onset

The following summaries with 95% exact CIs using Clopper Pearson method, based on events recorded during the 8 days post each vaccination will be provided as the analysis of primary safety endpoint:

- Solicited Local AEs by Severity
- Solicited Systemic AEs by Severity

All MAAEs and PIMMCs after the first dose of IP will be summarized in a table by SOC, PT and Severity.

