In all by-severity summaries, the severity that will be presented represents the greatest severity captured in the eCRF if a subject reported multiple occurrences of the same AE. The possible severities include "Mild", "Moderate" and "Severe". The missing severity will be imputed as "Severe".

In all by-relationship summaries, the relationship that will be presented represents the greatest relatedness captured in the eCRF if a subject reported multiple occurrences of the same AE. The possible relationship includes "Related" and "Unrelated". The missing relationship will be imputed as "Related".

All AEs will be included in a data listing containing all subject-level data collected in the eCRF. All SAEs, all AEs leading to study withdrawal, MAAEs, PIMMCs and severe AEs will be listed separately.

A listing of SAEs and MAAEs, including a subset of specific PIMMCs for 12 months after the last dose of study vaccine will be presented in the addendum to the CSR once the study is complete.

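### The study-withdrawal AE endpoint misses AEs that stop vaccination in subjects who stay in follow-up, and no planned output links an AE to a lost dose

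*Protocol*

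**What the plan says.** The endpoint in Protocol 7.2 is "Occurrence of any AEs leading to study withdrawal", and SAP 3.2.2.1 repeats it. The planned outputs stay within that category:

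- Protocol 7.7.4.1: "AEs leading to study withdrawal will be summarized by study group", broken down by system organ class and preferred term.
- SAP 9.1, overview table: a row for "AE leading to study withdrawal, AE leading to death" and so on, with no row for AEs that end vaccination.
- SAP 9.1, listings: "all AEs leading to study withdrawal, MAAEs, PIMMCs and severe AEs will be listed separately".

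Elsewhere the protocol distinguishes two states. Section 4.2.1 speaks of withdrawal from the study or from study treatment, and 4.2.2 gives each its own follow-up. Section 4.3 gives AE-based grounds for withholding further doses: a serious or intolerable AE, and an ALT or AST elevation of Grade 2 or more that has not resolved within the visit window. Footnote p of Tables 12–1 and 12–2 adds an AE of Grade 3 or more that has neither returned to baseline nor stabilized. Section 4.3 then says: "All subjects who discontinue from study treatment prematurely will follow the same visit schedule as other subjects".

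One passage runs against this distinction. Protocol 10.2.2 says that significant deviations "may lead to the subject being withdrawn from the study (ie, no longer receive IP, see Section 4.2", which treats the two states as one.

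**The concern.** In a series of two or three doses, an obvious safety question is how many recipients could not complete the series because of an AE after an earlier dose. The only planned category that ties an AE to stopping anything is study withdrawal. Because the protocol tries to keep subjects in follow-up after vaccination stops, good retention moves these cases out of the endpoint. Two groups with the same number of AE-related lost doses could then show different endpoint counts only because their retention differed. A low count could also be taken to mean that few subjects were prevented from completing the series.

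**Working it through.** **1. Where a dose lost to an AE would appear, if the subject stays in the study**

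| Planned output | What it shows | AE linked to the lost dose? |
|---|---|---|
| Study-withdrawal summary, overview row and listing (Protocol 7.7.4.1, SAP 9.1) | AEs after which the subject left the study | Subject not included |
| General AE tables by dose, severity and relationship, and AE listings (SAP 9.1) | The AE itself | No link described |
| Disposition (SAP 5.1) | Numbers treated at each dose; reasons for not completing the Day 142 or Day 262 visit; in the addendum, reasons for leaving the study | No reason for a missed dose |
| Exposure (Protocol 7.7.6, SAP 7.2) | Numbers receiving 1, 2 or 3 doses; listing of administration details | No reason for a missed dose |

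The AE and the missed dose are each reported, but the connection between them is not.

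**2. The plan's own safety figures**

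Protocol Table 7–1 gives the chance of seeing at least one event, 1 − (1 − p)^n. For n = 60:

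- p = 1%: 1 − 0.99^60 = 45.28% (table: 45.3)
- p = 2%: 1 − 0.98^60 = 70.24% (table: 70.2)
- p = 5%: 1 − 0.95^60 = 95.39% (table: 95.4)

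All 14 entries reproduce. The table does not address this endpoint; only its formula and the group size of 60 are used below.

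**3. Illustration with assumed counts**

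Suppose 3 of 60 subjects in a group lose a dose to an AE and m of them stay in the study. The endpoint reports (3 − m)/60:

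- m = 0: 3/60 = 5.0% (exact 95% CI 1.0–13.9%)
- m = 1: 2/60 = 3.3%
- m = 2: 1/60 = 1.7%
- m = 3: 0/60 = 0% (exact 95% CI 0–6.0%)

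**4. Illustration with assumed rates**

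Let r be the true rate of AEs that cost a dose and s the share of those subjects who stay. The endpoint counts at rate q = r(1 − s). The expected count per group is 60q, and the chance of at least one counted subject is 1 − (1 − q)^60. Each cell gives the expected count and that chance.

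| r | s = 0 | s = 0.5 | s = 0.8 | s = 1 |
|---|---|---|---|---|
| 1% | 0.6; 45.3% | 0.3; 26.0% | 0.12; 11.3% | 0; 0% |
| 2% | 1.2; 70.2% | 0.6; 45.3% | 0.24; 21.4% | 0; 0% |
| 5% | 3.0; 95.4% | 1.5; 78.1% | 0.6; 45.3% | 0; 0% |

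Across 720 subjects, r from 1% to 5% means 720 × 0.01 = 7.2 to 720 × 0.05 = 36 affected subjects. The documents give neither r nor s.

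**The case against.** The strongest reply is that little is hidden. Reactogenicity is the primary safety endpoint and is reported by group and severity with exact intervals (Protocol 7.7.3.1, SAP 9.1). All AEs are tabulated by dose, severe AEs are listed separately, and Grade 2 or higher ALT and AST elevations are always entered as AEs (Protocol 6.2.5.3). Missed doses can be seen in the disposition and exposure counts. The study is descriptive, and pausing rules bring serious signals to the IDMC.

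Most of this stands, and it rules out some stronger readings:

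- A reader might infer that these AEs vanish from the report. They do not; only the link to the missed dose is absent.
- A reader might infer that the endpoint will be close to zero in every group. The documents do not support that. Section 4.2.1 allows an AE to lead to withdrawal from the study, and those subjects are counted. Section 4.2.2 only encourages later attendance after treatment stops, although 4.3 is firmer.
- A reader might infer from 10.2.2 that study withdrawal already includes stopping vaccine. That passage concerns protocol deviations, and 4.2.1, 4.2.2 and 4.3 keep the two states apart. It leaves an ambiguity to remove, with no predictable effect on the count.

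The reply does not close the gap. Matching an AE listing to a dosing listing by hand is no substitute for a count by group, and it cannot show that a given AE was the reason for a given missed dose unless that reason was collected. Pausing rules govern conduct and report no such count.

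**Conclusion.** The point holds as a modest reporting gap. The endpoint, its summary, its overview row and its listing leave out AEs that stop vaccination in subjects who remain in follow-up, and no other planned output supplies the connection. For an assumed 3 affected subjects in a group of 60, the endpoint shows anything from 3/60 (none stay) to 0/60 (all stay). The 0/60 end rests wholly on full retention and is not a forecast. No figure stated in either document changes, and neither the primary safety analysis nor the immunogenicity analyses are called into question.

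**What to change.** - In Protocol 7.2 and 7.7.4.1 and SAP 3.2.2.1 and 9.1, keep the study-withdrawal category and add beside it AEs leading to discontinuation of IP or to a planned dose not being given. Report the two separately, by study group and preceding dose, in the SAP 9.1 overview, and add a listing.
- Confirm that the eCRF holds the reason for each missed dose and its link to an AE. This cannot be assumed. Protocol 5.3.2 says "Reasons for departure from the expected dispensing regimen must also be recorded", but as part of product accountability records. Section 4.2.2 names an eCRF page for the reason for leaving the study only. The action taken is collected for solicited reactions (6.2.5.2) but is not among the items in 6.2.5.4 for AEs in general. If the field is missing, add it.
- Reconcile the parenthesis in Protocol 10.2.2 with 4.2.1, 4.2.2 and 4.3, so that study withdrawal has one meaning for sites and programmers.

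The cost is some wording, one overview row, one listing and possibly one data field. The reported rate may look less favourable. No visit, revaccination criterion or other clinical rule changes.
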